15.1 Sample Size Rationale

EVEC is an exploratory study, as such the sample size was considered secondary to the ability of the study to provide exploratory information concerning the objectives. In addition, we lack good preliminary data on the exploratory outcomes and PROs for assessing sample size. Therefore, for illustrative purposes we have limited our power analysis to an evaluation of monthly migraine days based upon the results observed in the PROMISE trials and Phase IIIa

studies of other medications to be evaluated in EVEC. In the [Panel 5](#) below we describe the effect size observed in the PROMISE 1 and 2 trials:

Panel 5 Effect Sizes Observed in Promise Trials

Study	SD*	Epti dose vs placebo	Effect Size (ES; MMDs)	Standardized Effect Size (SES)
Promise 1 (episodic)	3.0	30mg	-0.82	0.27
		100mg	-0.69	0.23
		300mg	-1.11	0.37
Promise 2 (chronic)	5.7	100mg	-2.0	0.36
		300mg	-2.6	0.45

Note that in EVEC, it is expected that most patients will initiate treatment on the 100 mg dose.

The primary hypothesis will be tested using the following regression model:

$$Y = \beta_0 + \beta_1 x_1 + \beta_2 x_2 + \beta_z x_z + \epsilon$$

Where “Y” is the number of migraine days accumulated from treatment initiation to the final day of week 12 (and 24), This “area under the curve” (AUC) calculation will provide more power than the PROMISE calculations which were based upon the change between the baseline month and the final month of observation. β_1 is the coefficient associated with the number of migraine days reported in the month proceeding screening, and β_2 is the coefficient associated with treatment group assignment (i.e., eptinezumab or other advanced preventive medications). B_z is the coefficient associated with the vector of other covariates that might be considered for inclusion in the model to control other sources of variation (i.e., botox assignment, age, gender, etc.).

The loss to follow-up in the Promise trials was less than 10%. As this is a pragmatic real-world trial with patients receiving free medication and having the opportunity to change treatments without penalty, we expect to have a similarly modest loss to follow-up.

Panel 6 Sample size and Power from PROMISE Trials Assumptions

Standardized Effect size (SES)	N per arm	Power
0.23 (Promise 1)	100	37%
	150	51%
	200	63%
0.30 (average)	100	56%
	150	74%
	200	85%
0.36 (Promise 2)	100	72%
	150	88%
	200	95%

As would be expected in a pragmatic trial, the sample size of EVEC (100 persons per arm) is a function of the project budget and timeliness. In [Panel 6](#) we illustrate the expected power based upon the assumptions developed from PROMISE 1 and 2. We have highlighted the 100 per arm for the PROMISE 2 effect size. If, as expected, we meet the PROMISE 2 assumptions, we will have at least 72% power to demonstrate a standardized effect of 0.45. Given that we believe that the effect size will be larger in EVEC than observed in PROMISE 2, even as we pool patients with episodic and chronic migraine, we expect to have a practical power in excess of 80% to find a difference between eptinezumab and the other advanced preventive medications with an alpha of 0.05.

16 Statistical Software

Analyses will be conducted using SAS[®], Version 9.4 or later and R[®], Version 4.2.1 or later.

17 Changes to Analyses Specified in the Protocol

N/A

18 Details on Data Handling

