#### **5.5 Withdrawal Criteria**

Information on participants who withdraw from the study will be collected in the withdrawal section of the CRF.

A participant must be withdrawn from the study if:

- the participant withdraws their consent (defined as a participant who explicitly takes back their consent); section [8.9](#) states how the patient's data will be handled
- the participant is lost to follow-up (defined as a participant who fails to comply with scheduled study visits or contact, who has not actively withdrawn from the study, and

for whom no alternative contact information is available [this implies that at least two documented attempts have been made to contact the patient])

- the investigator considers it, for safety and/or study compliance reasons, in the best interests of the participant that they be withdrawn from treatment
- All participants will be permitted to withdraw at their choice or upon advice of their treating physician. Information collected from the participant prior to withdrawal will remain in the study data set.

No participant will be withdrawn from the study due to non-compliance with treatment. As this is a pragmatic real-world study, the failure to comply with treatment is considered a real-world outcome. However, an investigator may withdraw a participant from the study based upon their medical judgement if they deem continued involvement in the study is detrimental to the participant's welfare.

Products purchased with study-specific vouchers cannot be used for an off-label indication. Participants must meet the criteria for CM at baseline in order to be randomized to onabotulinumtoxinA (Botox®). Participants who do not comply with this requirement will be withdrawn from the study.

Participants who become pregnant will be withdrawn from the study and counselled to enroll in the Lundbeck pregnancy registry. The Lundbeck pregnancy registry is a prospective, observational study in the United States that will be initiated prior to the end of this trial.

Participants who withdraw will not be replaced.

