#### **6.3.1 Change in Treatment**

Participants may switch to an alternative preventive treatment in either treatment cohort after they have received their initial treatment with the medication to which they were randomized. Such a decision may be made upon recommendation of their treating clinician or participant preference. The site staff will investigate the reason for treatment change with both the treating clinician and participant. The use of medications, including gepants, for relief of acute migraine symptoms in either treatment arm is permitted and will be recorded in the smartphone application.

For all participants, the treatment to which they are initially assigned must be the treatment given at Baseline (Visit 2). Switching of medication is not permitted prior to administration of the first dose of medication. For participants who receive eptinezumab or Botox as their initial treatment and elect to switch to a subcutaneous anti-CGRP injectable (i.e., erenumab, fremanezumab or galcanezumab), they may not do so until week 12 (visit 5), after the treatment window for their initial treatment has ended. Participants who receive eptinezumab or Botox at week 12 (Visit 5) will not be permitted to switch their treatment for the remaining duration of the study.

Participants initially treated with a subcutaneous anti-CGRP injectable may only switch to eptinezumab, or Botox at week 12 (visit 5) due to the design of the study. However, these participants may switch to another of the subcutaneous anti-CGRP injectable medications at any time, once the treatment window for their previous injection has ended.

No changes in treatment will be permitted after Visit 7.

All changes in treatment are to be documented in the eCRF.

If a participant wishes to switch their medication, but does not meet the specified criteria to do so, as stated above, they should be withdrawn from the study and be treated as per standard of care by their physician.

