#### 16.3.2 Sample Size and Power

EVEC is an exploratory study, as such the sample size was considered secondary to the ability of the study to provide exploratory information concerning the objectives. However, for illustrative purposes we provide the power analysis here. Based upon the PROMISE trials and Phase IIIa studies of other medications to be evaluated in EVEC we expect to see a 2-day difference in the average monthly migraine days (MMD) at 13 weeks and a standard deviation of 6.0 around this measure. Based on this we expect to have 83% power to assess this difference with a sample size of 200 participants, assuming no significant loss to follow-up.

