3.3 Definition of Withdrawal

Withdrawal from the study is defined as termination of consent on or before Visit 8. Participants who withdraw from the study prior to Visit 8 will be asked to complete an Early Termination Visit. The visit must be scheduled as soon as possible after withdrawal. All information collected at an Early Termination Visit is to be recorded in the Visit 8 forms of the electronic case report form (eCRF). If the patient denies completing the Early Termination Visit, then no further data will be collected.

No participant will be withdrawn from the study due to non-compliance with treatment. As this is a pragmatic real-world study, the failure to comply with treatment is considered a real-world outcome. However, an investigator may withdraw a participant from the study based upon their medical judgement if they deem continued involvement in the study is detrimental to the participant's welfare.

No new information will be collected from participants who withdraw from the study, except information collected in relation to the scheduled Withdrawal Visit or needed for the follow-up of adverse events.

The reason for withdrawal must be recorded in the eCRF.

For a participant who withdraws consent:

- If the participant withdraws consent during a visit and then agrees to it being the final visit, the investigator will complete the visit as a Withdrawal Visit and all the data collected up to and including that visit will be used
- If the participant withdraws consent during a telephone conversation, the investigator will ask the participant if they might attend a Withdrawal Visit. If the participant:
 - Agrees to attend a Withdrawal Visit, all the data collected up to and including that visit will be used
 - Refuses to attend an Early Termination Visit, the investigator should attempt to follow the participant's safety and future treatment; any information collected will only be recorded in the patient's medical records

If the participant explicitly requests that their data collected from the time of withdrawal of consent onwards not be used, this will be respected.

The end of the study for an individual participant is defined as the last protocol-specified contact with that patient. The overall end of the study is defined as the last protocol-specified contact with the last patient ongoing in the study.

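### The 72% power in SAP 15.1 is a zero-loss figure for effect 0.36: it makes no allowance for the loss the section itself expects, and the text pairs it with the wrong effect size (0.45)

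*SAP*

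**What the plan says.** SAP 15.1 gives the EVEC sample as 100 per arm, set by budget and timelines. Panel 6 lists 72% power for a standardized effect of 0.36 at 100 per arm. The text below it reads "If, as expected, we meet the PROMISE 2 assumptions, we will have at least 72% power" and names 0.45 as the effect to be shown.

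On attrition, the same section says "The loss to follow-up in the Promise trials was less than 10" percent. Of EVEC participants it says that, with free medication and "having the opportunity to change treatments without penalty, we expect to have a similarly modest loss to follow-up". It gives no exact loss figure, no inflation of the sample and no number expected to be evaluable.

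Elsewhere:
- Protocol 16.3.2 gives its own power figure on the condition "assuming no significant loss to follow-up".
- Protocol 5.5: "Participants who withdraw will not be replaced".
- SAP 3.3: "No new information will be collected from participants who withdraw from the study", apart from the withdrawal visit and adverse-event follow-up.
- Protocol 6.3.1 (and SAP 3.4 in the same terms), on participants who want a switch outside the permitted windows: "they should be withdrawn from the study and be treated as per standard of care by their physician".

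**The concern.** A power figure should refer to the number of participants who will inform the analysis. Here 100 per arm is both the number enrolled and the number used in the calculation, although some loss is expected and cannot be made up by replacement. The wording presents 72% as a minimum. For the Panel 6 row it comes from, it is the value at zero loss.

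The two documents also differ. The protocol discloses a no-loss condition, while the SAP expects loss and states no condition. The SAP's reason for expecting little loss is that treatment can be changed freely, which sits badly with rules that withdraw anyone seeking a change outside the windows.

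What is at stake is how readers judge the size of the study. SAP 15.1 goes on from the 72% to expect a practical power above 80%.

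**Working it through.** **Inputs.** Two-sided 5% level (alpha in SAP 15.1, sidedness in SAP 11.2.2). Enrolled n = 100 per arm (SAP 15.1). Allocation of eptinezumab to pooled comparators is 1:1, since episodic is 1:1 and chronic is 3:(2+1). Effects are 0.36 (Panel 6) and 0.45 (SAP 15.1 text). Loss is under 10% (SAP 15.1); I use 5% and 10%, with 10% as the upper limit.

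**Formula.** Power = Φ(δ√(n/2) − 1.96), checked against the noncentral t.

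**Reproducing the plan.** For δ = 0.36 and n = 100: 0.36 × √50 = 2.546; 2.546 − 1.96 = 0.586; Φ(0.586) = 72.1% (t: 71.7%). All nine Panel 6 entries reproduce to rounding with the full n per arm. A one-sided test would give 81.6%, so it was not the method used. Panel 6 therefore contains no attrition allowance.

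**Applying the expected loss**, with n = 100 × (1 − loss) and leavers contributing nothing:

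| Effect | Loss | n per arm | δ√(n/2) − 1.96 | Power, normal | Power, t |
|---|---|---|---|---|---|
| 0.36 | 0% | 100 | 0.586 | 72.1% | 71.7% |
| 0.36 | 5% | 95 | 0.521 | 69.9% | 69.4% |
| 0.36 | 10% | 90 | 0.455 | 67.5% | 67.1% |
| 0.45 | 0% | 100 | 1.222 | 88.9% | 88.6% |
| 0.45 | 5% | 95 | 1.141 | 87.3% | 87.0% |
| 0.45 | 10% | 90 | 1.059 | 85.5% | 85.1% |

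The cost at 0.36 is 72.1 − 69.9 = 2.2 points at 5% loss and 72.1 − 67.5 = 4.6 points at 10%.

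**The effect-size pairing.** Panel 5 gives 0.36 for PROMISE 2 at 100 mg and 0.45 at 300 mg. Panel 6 has no row for 0.45. The text takes 72% from the 0.36 row and attaches it to 0.45, for which the same formula gives 88.9%.

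**Protocol figure.** I do not scale the protocol's 83% for loss. Its stated inputs (2 days, SD 6.0, so δ = 0.333) at 100 per arm give 65.4% by the same formula, so 83% rests on something not stated there. That is a separate matter.

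**The case against.** The strongest reply is that the sentence as printed is not false. Read with its own effect of 0.45, power is 85.5% even at 90 per arm, so a claim of at least 72% survives the expected loss. That stands: the words are wrong only for the 0.36 row the figure comes from. The defect in the sentence is then the pairing, and the loss correction has to be made together with it. Printing 67% while leaving 0.45 in place would create a new error.

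Second, leavers are not simply dropped. A reader might infer that the accumulated migraine-day total does not exist for anyone who leaves early. The SAP does not say that:
- The full analysis set (section 4) needs only one daily report after treatment.
- Section 18.15.1 prorates weeks with at least four reported days and counts missing days as migraine days in sparser weeks.
- Section 11.2.3 aims to impute so that all observations with missing outcomes can be used.

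So zero contribution is an assumption made for the calculation. On the other side, the multiple-imputation plan in 11.2.6 does not name migraine days, and the SAP does not say whether the fill-in rule runs on after withdrawal. The documents do not show that these rules recover the lost power, and their effect cannot be quantified from what is given.

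Third, the regression in 15.1 adjusts for prior-month migraine days, while Panel 6 is a plain two-sample calculation. A 10% reduction in residual variance (a correlation of about √0.10 = 0.32, assumed) would offset a 10% loss exactly. That is fair, and it is why the loss-adjusted figures are stated before any such gain.

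Fourth, both documents label the power illustrative, and SAP Panel 1 does not list migraine days among the endpoints. This limits the severity.

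**Conclusion.** The point holds in limited form and is minor. At effect 0.36, 72% requires all 100 enrolled per arm to be analysed. Under the section's own expectation of loss below 10%, power lies between about 67% and 72%, a shortfall of at most about 5 points. This assumes that loss is equal in the two arms, that leavers contribute nothing and that covariate adjustment gives no gain. Separately, 72% is attached to the wrong effect size.

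A reader might infer that true power is below 67%, on the ground that forced withdrawals for switches outside the windows push loss to 15% or 20%. The documents give no such figure. With loss below 10%, about 67% is the bottom of the range in this calculation. The conflict between the low-loss rationale and the switching rules is real, but its size cannot be derived from the text.

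**What to change.** In SAP 15.1:
- Pair 72% with effect 0.36, not 0.45.
- Delete *at least*.
- State the evaluable number per arm that each power figure assumes.
- Print about 67-70% for 5-10% loss at effect 0.36 and, if 0.45 is kept in the text, about 85-87% for the same loss.

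In Protocol 16.3.2, replace the no-loss condition with the same loss assumption.

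Reconcile the SAP 15.1 rationale about changing treatment freely with the withdrawal rule in Protocol 6.3.1 and SAP 3.4. Which text should give way is for the sponsor.

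The cost is a few sentences in each document and a slightly less favourable figure. No change to enrolment or to the analysis model is needed for this point.

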18.1 Time from Scheduled Daily Report to Patient Reporting Time

If the time from the scheduled daily report on the eDiary to the reporting time of the patient exceeds >24 hours, then the patient report will be considered invalid, and all relevant data are considered missing.

18.2 eDiary

Compliance to the eDiary between the Screening and Baseline visits will be measured as the proportion of days in which the patient accessed the eDiary and responded to the question “In the last 24 hours did you have a headache?” within the time interval between the Screening visit and Baseline visit (inclusive of the days of the Screening and Baseline visit).

18.3 Good Day/Bad Day Scale (Week 1-4, 1-12, and 1-24)

The Good Day/Bad Day Scale measures patients’ global perception of the effect of symptoms on the life of people living with migraine by asking how many “good days” and “bad days” they had over the past week. The total number of days reported is required to total 7 (i.e, the sum of the number of good days and bad days must equal 7).

The Good Day/Bad Day scale is reported weekly. If the total number of days reported is <7 for a given week, then the number of good days will be considered as missing. Missing values will be imputed using multiple imputation methods based on the amount and pattern of missing data.

18.4 PI-MBS (weeks 1-4, 1-12, and 1-24)

Patients will report their most bothersome symptom associated with a headache including pain worsened by physical activity, throbbing head pain, nausea, vomiting, photophobia, phonophobia, difficulty concentrating, visual aura, other aura, or the patient may specify other symptoms. For the most bothersome symptom, patients will be asked to rate its severity ranging from mild (1) to severe (3). The PI-MBS data will be captured daily via the smartphone app when participants are prompted to report if they had a headache. The PI-MBS and severity will be descriptively summarized, and missing data will not be imputed.

18.5 EQ-5D-5L (weeks 1-4, 1-12, and 1-24)

The EQ-5D-5L is a patient-reported assessment designed to measure the patient’s well-being.³ It consists of 5 descriptive items (mobility, self-care, usual activities, pain/discomfort, and depression/anxiety) and a visual analogue scale (VAS) of the overall health state. Each descriptive item is rated on a 5-point index ranging from 1 (no problems) to 5 (extreme problems). The VAS is scored separately and ranges from 0 (worst imaginable health state) to 100 (best imaginable health state). A single summary index (from 0 to 1) will be calculated based on item responses using the United States value set (EuroQoL).

The EQ-5D will be reported weekly, and a missing weekly value for the EQ-5D score will be imputed using multiple imputation methods based on the amount and pattern of missing data.

18.6 HCRU (weeks 1-4, 1-12, and 1-24)

All-cause medical HCRU will include outpatient physician visits, inpatient hospitalizations, urgent care visits, and emergency department visits. Medications (over-the-counter and

prescription) used for the acute relief and prevention of migraine will also be included. HCRU is reported by patients using the ePRO application on a daily basis and on the HCRU follow-up questionnaire, which is a comprehensive review of patient HCRU obtained by study coordinators during the monthly visits. Since the HCRU follow-up questionnaire contains more comprehensive information (i.e., patient reported HCRU and any that may not have been reported by the patient on the ePRO), the analysis will be based on the HCRU follow-up questionnaire. However, data reported in the ePRO and follow-up questionnaire will be compared to assess for inconsistencies. Missing values will not be imputed.

18.6.1 Medical HCRU

Medical HCRU will be ascertained based on the HCRU follow-up questionnaire. Reported counts of HCRU will be summed across weeks 1-4, 1-12, and 1-24 based on the date of reported healthcare utilization.

Reported HCRU will be stratified as outpatient (physician office visit, outpatient service use, outpatient surgery), urgent care visit, emergency room visit, and inpatient service.

18.6.2 Medication HCRU

Migraine medication HCRU (over-the-counter and prescription) will be ascertained based on the patient's reported medication use during the monthly follow-up visits in which the study coordinator reviews all reported medication use in addition to any unreported utilization. Reported counts of medications will be summed across weeks 1-4, 1-12, and 1-24 based on the reported start and discontinuation dates of the medication.

Medications will be classified as acute, or preventive stratified by drug class:

- Acute
 - Oral anti-CGRP
 - Triptans
 - Analgesics (opioids, non-narcotic, anti-inflammatory)
 - Barbiturate hypnotics
 - Ergots
 - 5-HT agonist
 - Isometheptene
 - Antiemetics
- Preventive
 - Anticonvulsants
 - Serotonin-norepinephrine reuptake inhibitor
 - Selective serotonin reuptake inhibitors
 - Tricyclic antidepressants
 - Antihistamines
 - Antihypertensives (angiotensin converting enzyme inhibitors, angiotensin receptor blockers, beta-blockers, alpha agonists, calcium channel blockers)

- NMDA antagonists
- Monoamine oxidase inhibitors

